11.1.2 ADVERSE EVENTS

Each AE and serious adverse event (SAE) term recorded on the CRFs by primary system organ class (SOC) and will be mapped to a preferred term (PT) using the MedDRA dictionary. The Investigator will assess AE severity and relationship to the study treatment.

A treatment-emergent adverse event (TEAE) is defined as any AE with an onset date on or after the date of the first study treatment, or any ongoing event started on the date of the first dose that worsens in severity. Only AEs with an onset date prior to the date of the last dose + 30 days will be tabulated in summary tables. For the purpose of calculating treatment emergence and inclusion in summary tables, incomplete onset dates will be imputed as detailed in Appendix B.

AEs will be summarized by the number and percent of patients in each primary SOC and PT. Patients will be counted only once for each primary SOC and each PT. Summary tables of AEs by primary SOC, PT and intensity will be provided. If a patient has more than one AE coded to the same PT, the patient will be counted only once for that PT by using the event with the highest intensity. Similarly, if a patient has more than one AE within a primary SOC category, the patient will be counted only once in that SOC category by using the event with the highest intensity. AEs by primary SOC, PT and relationship to study drug will be provided as well. If a patient has more than one AE coded to the same PT, the patient will be counted only once for that PT by using the most related event. Similarly, if a patient has more than one AE within a primary SOC category, the patient will be counted only once in that primary SOC category by using the most related event. In addition, SAEs by primary SOC and PT will be provided. Deaths and SAEs will be summarized similarly to AEs. All AE tables will also include the total number of events, counting multiple events per patient.

Injection-related AEs, other (non-injection related) AEs as well as all AEs will be presented. Summaries of these AE subsets will be presented for the following categories:

- Study drug-related
- Intensity
- Serious
- AEs which led to treatment/study discontinuation
- SAEs which led to treatment/study discontinuation
- AEs occurring in 5% or greater of patients (by preferred term)

In the AE summary, the SOCs and the PTs within each SOC will appear in descending order of frequency.

Frequencies of deaths and hospitalizations will also be summarized.
Other safety analyses will be performed as appropriate

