9.4.1. Adverse Events and Serious Adverse Events

The following definitions, developed in accordance with the United States (US) Code of Federal Regulations (CFR) and the International Conference on Harmonization (ICH) Clinical Safety Data Management Guidance for Industry, E2A, will be used for the purpose of identifying AEs in this clinical study.

An AE is any untoward medical occurrence in a subject administered a pharmaceutical product that does not necessarily have a causal relationship with this treatment. An AE can therefore be any unfavorable and unintended sign (e.g., including an abnormal laboratory finding), symptom, or increase in severity of a preexisting abnormality, temporally associated with the use of a medicinal (investigational) product, whether or not considered related to the medicinal (investigational) product.

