9.4.1.1. Adverse Event Reporting

All AEs (except for withdrawal symptoms, see below) must be entered on the AE CRF, regardless of causality or severity. AEs include new AEs, worsening baseline conditions, clinically significant laboratory findings, disease-related signs and symptoms that were not present at baseline, and any events or findings that the Investigator feels are clinically significant. Withdrawal symptoms will be captured via specified assessments and should not be recorded as AEs.

Disease-related signs and symptoms that are present at baseline should not be recorded as AEs unless they worsen in severity or increase in frequency.

Information collected concerning AEs will include the following:

- Name of the event
- Onset date
- Resolution date
- Severity (i.e., mild, moderate, or severe)
- Relationship to study drug
- Action and outcome
- Seriousness of event

Definition of MILD, MODERATE, SEVERE AE:

- Mild- An AE that requires minimal treatment and does not interfere with daily living.
- Moderate- An AE that requires therapeutic intervention and interferes with daily living.
- Severe- An AE that requires intensive therapeutic intervention, significant, etc.

All AEs will be documented and followed from the time the subject has signed the ICF until 14 days after the Follow-up Visit (or 30 days after early termination). Serious AEs and AEs that have been designated as possibly related to study drug will be followed until resolution or stabilization.

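### SAP 11.1.2: the worsening clause of the TEAE definition adds nothing to the onset clause, so a pre-dose AE kept as one record that worsens on CAM2038 is not classed as treatment-emergent

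*SAP*

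**What the plan says.** SAP 11.1.2 builds the TEAE definition from two clauses. The onset clause is "any AE with an onset date on or after the date of the first study treatment". The worsening clause follows: "or any ongoing event started on the date of the first dose that worsens in severity". The next sentence limits the tables: "Only AEs with an onset date prior to the date of the last dose + 30 days will be tabulated in summary tables". The section then names treatment emergence and inclusion in tables as two uses of the imputed dates in Appendix B, without saying that one depends on the other. No AE table title in Appendix A uses the term treatment-emergent. On deaths the section says "Deaths and SAEs will be summarized similarly to AEs" and, later, "Frequencies of deaths and hospitalizations will also be summarized".

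In the protocol, AEs are recorded from consent (Table 3, footnote u; 9.4.1.1), and screening falls 1 to 3 weeks before Day 1 (7.1.1). Section 9.4.1 counts an "increase in severity of a preexisting abnormality" as an AE, and 9.4.1.1 states: "AEs include new AEs, worsening baseline conditions, clinically significant laboratory findings". The item list in 9.4.1.1, opened by "Information collected concerning AEs will include the following", has one onset date, one resolution date and one severity grade, and no date of change in severity. Collection ends 14 days after the Follow-up Visit, or 30 days after early termination.

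**The concern.** A worsening clause is there to bring in conditions that existed before the drug and became worse on it. This one refers to events that began on the day of first dose, which are treatment-emergent without it. The events it would be needed for, those recorded during screening, fall under neither clause.

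Safety is the primary objective, and the study is single-arm and descriptive. The TEAE flag is therefore the main means of separating what happened on CAM2038 from what was there before. As written, the same clinical course is or is not treatment-emergent according to whether the site updates an existing AE record or opens a new one.

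**Working it through.** **1. Do the two start dates differ?** The onset clause runs from first study treatment, the worsening clause from first dose. For new entrants the sublingual test dose and the first CAM2038 injection are both given on Day 1 (Protocol 7.1.2.1). Other patients have no test dose. The two dates coincide; call the date D.

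**2. The clauses as conditions.**
- Onset clause: onset ≥ D.
- Worsening clause: onset = D, and ongoing, and worsens.

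Any onset equal to D satisfies onset ≥ D, so every event that meets the second condition meets the first. A check over all combinations of onset day (−30 to 399), ongoing or not, and worsening or not found no event that meets the worsening clause alone.

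**3. Cases.**

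| Event | TEAE as written | TEAE with the clause reworded to onset before D |
|---|---|---|
| Onset on or after D | Yes | Yes |
| Onset before D, does not worsen | No | No |
| Onset before D, worsens on drug, kept as one record | **No** | **Yes** |
| Onset before D, worsening entered as a new AE with its own onset date | Yes (new record) | Yes (new record) |

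**4. Can the third case arise?** The period from screening to Day 1 is 7 to 21 days per patient, and AEs are recorded from consent. Appendix B of the SAP places some partial onset dates before first dosing, so the SAP itself expects pre-dose AE records. The protocol makes a worsening recordable, but gives no rule for an AE already on the CRF.

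**5. Effect on the tables.** The inclusion sentence in SAP 11.1.2 has an upper limit and no lower one.

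| Scope of tables | One-record pre-dose AE that worsens | AE that began and ended before CAM2038 |
|---|---|---|
| Limited to TEAEs, clause as written | Left out | Left out |
| Not limited to TEAEs | Counted | Counted |
| Limited to TEAEs, clause reworded | Counted | Left out |

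Only the last row gives the right answer in both columns.

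**6. The upper cut-off (secondary).** Nominal day of Week w = 1 + 7(w − 1).
- Last q4w injection, Week 45 (Protocol Table 3, footnote g): Day 309. Last q1w injection, assumed at Week 48: Day 330.
- Follow-up, Week 53: Day 365. End of collection: 365 + 14 = Day 379.
- First onset not tabulated: q4w 309 + 30 = Day 339; q1w 330 + 30 = Day 360.
- Collected but not tabulated: q4w 379 − 339 = 40 days; q1w 379 − 360 = 19 days (41 and 20 if the end day is counted).

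Sensitivity:
- Follow-up at Week 52, as in the synopsis, ends collection on Day 372 and gives 33 and 12 days.
- Visit windows on the last dose, with Follow-up held at Day 365, give 33 to 47 (q4w) and 16 to 22 (q1w).
- A q1w booster in Week 46, 47 or 48, counted as a dose, reduces the q4w figure to 33, 26 or 19.
- For a patient who terminates k days after the last dose, the figure is (k + 30) − 30 = k days.

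**The case against.** The best defence is that the protocol already solves the problem. Sections 9.4.1 and 9.4.1.1 make a worsening an AE in its own right, and a list with one onset date and one severity fits a new entry better than a record that changes. A new entry on drug meets the onset clause. On this view the clause is a drafting slip for an event ongoing at first dose, with no consequence. Much of this stands: it narrows the gap to an AE already entered during screening, still ongoing, worse on drug, and not re-entered. It does not close the gap, because neither document requires re-entry.

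Two stronger readings might be inferred.

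- **That on-drug worsening disappears from the safety tables.** The documents do not support this. It needs both one-record entry and tables limited to TEAEs, and the SAP states neither.
- **That the 30-day cut-off is wrong, or hides late deaths and SAEs.** This is not supported either. Thirty days exceeds the SAP's own exposure allowance of 28 days (q4w) or 7 days (q1w). Late events remain in the listings. For completers on the nominal calendar, every excluded day (from Day 339 or 360) follows the Week 49 move to standard care (Day 337). Of the excluded days, 14 also follow the last scheduled visit, leaving 365 − 339 = 26 (q4w) or 365 − 360 = 5 (q1w) before it. For deaths, one sentence in 11.1.2 ties them to the AE rules, while the separate frequencies sentence and the titles of Tables 14.3.9.1 and 14.3.9.2, which say all, point the other way. That is an ambiguity, not a shown exclusion.

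**Conclusion.** The worsening clause is wrong as written: it has no effect, and a pre-dose AE that worsens on CAM2038 under one record is not treatment-emergent. This follows from the text alone and needs no assumption beyond the shared Day 1 date.

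The consequence is less certain. It depends on how sites record worsening and on whether the tables are limited to TEAEs, and the documents settle neither. The number of events cannot be derived. It is probably small, since each must begin within a 7- to 21-day period, be ongoing at first dose, worsen, and not be re-entered. The correction is worth making because the rule serves the primary objective and the change is one phrase.

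The untabulated 40 or 19 nominal days are a reporting choice and not an error. The unclear scope of the death and hospitalization tables needs one clarifying sentence.

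**What to change.** 1. Reword the worsening clause of SAP 11.1.2 to: *an event that began before the date of first dose and becomes more severe on or after that date*.
2. State that the AE summary tables are limited to TEAEs, so that events over before any CAM2038 are not counted. Make this change together with the first; alone, it would drop the one-record worsening events.
3. Check whether the CRF dates changes in severity. If it does not, instruct sites to enter on-drug worsening of an existing AE as a new record, and leave the pre-dose record at its pre-dose severity so that the event totals do not count it twice.
4. State whether the 30-day cut-off applies to Tables 14.3.9.1 to 14.3.9.6.
5. Optional: add a separately labelled post-treatment summary of SAEs and deaths with onset from 30 days after last dose to the end of collection. Do not pool it with the 30-day tables. The time from last dose to the end of collection differs by product (379 − 309 = 70 days for q4w, 379 − 330 = 49 for q1w), and for completers it includes standard care.

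The cost is one phrase, two sentences of scope, a derived flag, possibly a data-entry instruction with queries on existing records, and, if the option is taken, a few tables from data already collected.

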11.1.3 LABORATORY ASSESSMENTS

Chemistry, hematology, urinalysis and coagulation profile will be assessed at baseline and over time. Summary statistics for these parameters will be presented by visit for the actual value and change from baseline for each test in each laboratory category (hematology, chemistry, urinalysis, and coagulation profile). Shift tables will be presented for shifts from baseline lab categories to end of study laboratory

category. The three laboratory categories will be: L (below lower bound of normal range), N (within normal range), and H (above higher bound of normal range).

If a lab value is reported using a non-numeric qualifier (e.g., less than (<) a certain value, or greater than (>) a certain value), the given numeric value will be used in the summary statistics, ignoring the non-numeric qualifier.

If a patient has repeated laboratory values for a given time point, the value from the first evaluation at that time point will be used for summarization purposes. For the purpose of determining baseline, the last non-missing observation on or prior to first dose of CAM2038.

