^m A complete physical exam of all major body systems will be performed at the Screening Visit.

Study Phase:	Screening	Treatment Phase						EOT	Follow-up	
Treatment:	-	CAM2038 q1w or q4w	CAM2038 q1w			CAM2038 q4w				All Subjects
Study Population:	All Subjects ^a	All Subjects	New to BPN Treatment ^b	Transition from SL BPN/BPX ^c	Transition from CAM2038 q1w ^d	Transition from SL BPN/BPX (Monthly) ^e				
Month ^f :	M-1	M1	M1	M1 to Mx	M1 to Mx	Mx to M12 ^g	M1 to M12 ^h		M13	
Week ^h :	-3	W1	W1	W2 to Wx ⁱ	W1 to Wx ⁱ	Wx to W48	W1 to W48		W49	
Day:	-	Day 1	Day 2-7 ^j	-	-	-	-		-	
Weight, BMI	X	X		Monthly	Monthly	Monthly	Monthly			
Height	X									
Abbreviated Review of Systems		X							X	
Vital Signs ⁿ	X	X		Weekly	Weekly	Monthly	Monthly		X	
ECG	X			X ^o	X ^o	X ^o	X ^o		X	
Laboratory tests ^p	X								X	
Pregnancy Test ^q	X	X		Weekly	Weekly	Monthly	Monthly		X	
Hepatitis B/C, HIV ^r	X									
Injection Site Examination		X		Weekly	Weekly	Monthly	Monthly		X	
Dispense Treatment ID Card		X								
Urine Toxicology	X	X		Weekly	Weekly	Monthly	Monthly		X	
Illicit Drug Use Self-Report	X	X		Weekly	Weekly	Monthly	Monthly		X	
SOWS, COWS VAS	X	X	(X)	Monthly	Monthly	Monthly	Monthly		X	
EQ-5D-5L	X	X		Monthly	Monthly	Monthly	Monthly		X	

ⁿ Includes temperature, blood pressure, pulse rate, respiration rate.

^o ECG will be performed after the first administration of CAM2038 q1w or CAM2038 q4w (i.e., prior to dosing at Week 2 for CAM2038 q1w or Week 5 for CAM2038 q4w). During the study, ECGs will be performed after dose increases (excluding the initial dose titration and booster injections) and after intake of QT-extending drugs or CYP3A4 inhibitors.

^p Includes chemistry, hematology, urinalysis and coagulation profile.

^q A serum pregnancy test will be performed at Screening and EOT (Week 49). An “in-office” urine pregnancy test will be required at Day 1 PRIOR to the first injection of CAM2038 and then at each visit thereafter (for women of childbearing potential).

^r It is the Investigator’s responsibility to understand and comply with all laws and regulations that apply to HIV, Hepatitis B, and Hepatitis C and testing of blood. Hepatitis B/C and HIV testing is required unless a site’s IRB prohibits such testing.

Study Phase:	Screening	Treatment Phase						EOT	Follow-up
Treatment:	-	CAM2038 q1w or q4w	CAM2038 q1w			CAM2038 q4w			All Subjects

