9.4.3. Clinical Laboratory Assessments

All protocol-specified laboratory tests on blood and urine samples will be performed at a selected central laboratory, with the exception of urine pregnancy tests that are conducted at the study site. The central lab will generate laboratory reports and forward them to the clinical site in a timely manner. It is the responsibility of the Investigator to review and sign all lab reports expeditiously, in order to document appropriate safety monitoring of study subjects. The Investigator should sign and date each lab report concurrent with her or his review, and should indicate the clinical significance of each abnormal/flagged value by noting “NCS” (not clinically significant) or “CS” (clinically significant), for example. Notations indicating that a value is clinically significant should also include a brief description of the underlying disease or condition that is associated with the value, e.g., “CS/mild anemia.” Per investigator judgment, abnormal, clinically significant laboratory values are expected to be associated with an item recorded in medical history or with an AE.

Blood and urine samples will be collected, processed, and shipped according to instructions from the safety laboratory. Additional laboratory samples may be taken at the discretion of the Investigator if the results of any tests fall outside reference ranges or clinical symptoms necessitate testing to ensure safety. Specific hematology, coagulation, biochemistry, and urinalysis assessments are listed in [Table 4](#).

Table 4: Clinical Laboratory Assessments

Hematology	Biochemistry	Urinalysis
Hematocrit	Sodium	Color
Hemoglobin	Potassium	pH
Red blood cell (RBC) count	Magnesium	Specific gravity
RBC Morphology	Calcium	Ketones
Mean corpuscular volume	Glucose (random)	Protein
Mean corpuscular hemoglobin	Bicarbonate	Glucose
Mean corpuscular hemoglobin concentration	Chloride	Bilirubin
Total and differential (absolute) white blood cell count	Creatinine	Nitrite
Platelets	Total protein	Urobilinogen
	Blood urea nitrogen	Occult blood
	Albumin	Microscopic examination of sediment, only if urinalysis dipstick results are abnormal
	Total bilirubin	
	Alanine transferase	
	Aspartate transferase	
	Lactic dehydrogenase	
	Amylase	
	Lipase	
	Gamma-glutamyl transferase	
	Alkaline phosphatase	
	Creatine phosphokinase	
	Total cholesterol (non-fasting)	
Coagulation		
Prothrombin time (PT), International normalized ratio (INR)		

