11.3.3. Analysis of Safety Assessments

Exposure and safety summaries will be presented for both Safety Populations.

All AEs will be coded by primary system organ class (SOC) and preferred term according to the Medical Dictionary for Regulatory Activities (MedDRA), and summarized by number and percent of subjects in each primary SOC and preferred term. Summaries of these AE subsets will

be presented for relationship to study drug, intensity, seriousness, AEs or SAEs leading to discontinuation and AEs occurring in 5% or greater (by preferred term). Frequencies for deaths and hospitalizations will also be summarized.

Data for clinical laboratory tests, ECG, vital signs, and physical and injection site examinations will be summarized using standard descriptive and change from baseline statistics. Shift tables and tabular summaries of abnormalities will be provided, where appropriate. Medications will be coded using the World Health Organization Drug dictionary and summarized using descriptive statistics.

By-subject listings will be provided for all safety data.

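### Laboratory shift tables compare baseline with end of study only, so an abnormality found at an unscheduled on-treatment test and resolved by the final draw is tabulated as no shift

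*SAP*

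**What the plan says.** SAP section 11.1.3 states: "Shift tables will be presented for shifts from baseline lab categories to end of study laboratory" category. There are three categories: below, within and above the normal range. Baseline is "the last non-missing observation on or prior to first dose of CAM2038". When values are repeated at one time point, "the value from the first evaluation at that time point will be used for summarization purposes". The section also promises by-visit statistics for actual values and changes from baseline. It does not mention unscheduled samples.

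In the protocol's schedule of assessments (Table 3), the laboratory row is marked at Screening and once at the end; the weekly and monthly treatment columns are blank. Between those draws, protocol section 9.4.3 provides that "Additional laboratory samples may be taken at the discretion of the Investigator if the results of any tests fall outside reference ranges", or if symptoms call for it.

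On reporting, protocol section 11.3.3 says: "Shift tables and tabular summaries of abnormalities will be provided, where appropriate". Appendix A of the SAP lists laboratory data summaries and baseline shift tables for hematology, chemistry and coagulation. It lists no worst-value, any-time or abnormality table for laboratory tests.

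**The concern.** Laboratory tests are a named safety variable (protocol section 9.6), and the study's purpose is to describe safety over 48 weeks of treatment. With one scheduled draw after baseline, any laboratory evidence from within the treatment period comes from samples prompted by an abnormal result or by symptoms. These are the results a safety reader would most want to see, yet the shift table has no cell for them. A reader who sees a patient in the normal-to-normal cell cannot tell whether the patient stayed normal or had an abnormal result on drug that later resolved.

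The adverse event tables do not fully replace this. Under protocol section 9.4.3, the link from an abnormal value to an adverse event depends on the investigator's judgement. The adverse event tables count coded terms, not measured values against a reference range. The shift table is the planned laboratory tabulation that does not rest on that judgement.

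**Working it through.** The plan gives no figure to reproduce, and no sample-size or power formula applies. The check applies the SAP's rule to defined cases.

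**1. Which values can enter the shift table.** Baseline is the last value on or before first dose, which in practice is the Screening draw. The other end is the end-of-study draw. In the extracted schedule the columns are misaligned. I read the final laboratory mark as the end-of-treatment visit (Week 49), because the ECG row has its final mark in the same position and protocol section 9.4.5 places that ECG at end of treatment. Reading it as Week 53 changes nothing below. No value between the two draws can enter the table.

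**2. Applying the rule.** All cases start from a normal baseline (N); H is above range. To see whether the repeat-value rule matters, each case is run with the SAP's rule (first evaluation at the time point) and with a last-value alternative. The final column uses the highest value after first dose, including unscheduled and repeat samples.

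| Case | First evaluation (SAP) | Last value | Highest post-dose value |
|---|---|---|---|
| A. Unscheduled H; final N | N to N | N to N | N to H |
| B. Unscheduled H with normal repeat; final N | N to N | N to N | N to H |
| C. Final H, repeat N | N to H | N to N | N to H |
| D. Final N, repeat H | N to N | N to H | N to H |
| E. Unscheduled H; no final sample | none | none | N to H |

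Cases A and B are the concern. Both read as no shift under either repeat rule, so the cause is the restriction to two time points. The worst-value shift recovers both. In case A the lowest post-dose category is still N, which is why lowest and highest need separate tabulation.

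Case E shows a neighbouring gap: the SAP does not say what the end-of-study category is for a patient without a final sample. At the planned dropout this could concern up to 228 × 0.50 = 114 patients. The documents do not say how many of them will give a final sample.

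**3. Where else a case A result can appear.**
- By-subject listings: yes (protocol section 11.3.3; laboratory listings in Appendix A).
- Adverse event tables: yes, if the investigator judges it clinically significant (protocol sections 9.4.1.1 and 9.4.3; SAP section 11.1.2).
- By-visit statistics: not stated, since the SAP is silent on unscheduled samples.
- A laboratory abnormality table: none is listed.

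**4. Comparison within the SAP.** Section 11.1.6 summarises QT, QTcB and QTcF categories at each visit and also across any visit. Laboratory tests have no counterpart.

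**5. Size.** If k patients follow case A or B, the shift table shows none of the k episodes. Each is 1/228 = 0.4% of planned enrolment. Neither k nor the number of unscheduled samples is given, so k cannot be estimated.

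**The case against.** The strongest counter-argument is about ascertainment. The end-of-study shift rests on the one scheduled draw after baseline, so it compares patients on a common footing. A worst-value shift would mix patients with one post-dose value and patients sampled several times because something looked wrong. Its percentages would depend on how readily investigators test. This stands, and it is why the end-of-study table should stay and the added table needs a footnote and a count of patients with unscheduled samples. It is not a reason to leave the results untabulated. It also stands that the sparse schedule is the main limit on detecting transient change, which no extra table repairs.

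A reader might infer three stronger points that the documents do not support:

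- *That the first-evaluation rule helps hide resolved abnormalities.* It chooses among repeats at one time point, not between time points. Cases A and B are the same without it, and in case C it preserves the shift. It conceals an abnormality only in case D, which is not a resolved one.
- *That unscheduled values reach nothing but a listing.* Clinically significant findings are reportable as adverse events and tabulated as such, and the SAP's silence on unscheduled values in by-visit statistics is not an exclusion.
- *That the SAP breaks a protocol commitment.* Protocol section 11.3.3 qualifies the abnormality tables with where appropriate, and SAP section 11.1.2 leaves room for further safety analyses. The fair statement is that no such laboratory table is planned in Appendix A.

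**Conclusion.** The point holds as a gap in tabulation. An abnormality seen only at an unscheduled on-treatment test, and back in its baseline category by the final draw, is shown as no shift. Because only one laboratory draw after baseline is scheduled, this applies to the whole treatment period before that draw. The abnormalities most exposed are those judged not clinically significant, since the others should also appear as adverse events.

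The change is worth making, but no conclusion of the study is shown to depend on it, and the number of patients affected is unknown. The conclusion assumes that the laboratory row is marked only at Screening and at the end, and that end of study means the final draw. Reading it as the last available value would fill case E but leave cases A and B at no shift.

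**What to change.** In SAP section 11.1.3 and Appendix A, keep the end-of-study shift and add a shift from baseline to the worst value after first dose, with lowest and highest shown separately. Do this for hematology, chemistry and coagulation, the three groups that already have shift tables. Use all recorded results, including unscheduled and repeat samples. Show the number of patients with any unscheduled sample, and footnote that mid-treatment values are for-cause, so the percentages are not incidences. The first-evaluation rule can stay for the by-visit statistics.

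In the same edit, state how unscheduled values enter the by-visit statistics and what the end-of-study category is for a patient without a final sample.

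Cost: a few sentences, and three laboratory groups × two safety populations = 6 added tables. The downside is percentages that depend on investigator-directed testing. One point needs confirming: protocol section 9.4.3 sends protocol-specified tests to the central laboratory but does not say where discretionary samples are analysed. Any locally analysed result would have to be recorded with its own reference range before it could be classified.
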